Doses delayed by more than 2 hours should be skipped. Doses obscured by vomiting should not be re-administered. If more than 7 doses of the first 28 are missed due to noncompliance, the patient will be considered invaluable and study subject replaced. Patients with missed doses removed from evaluation will continue to be monitored for safety.

Duration of Therapy

Dosing is continued until

- 6 months from initiation of study drug. If dose is greater than 20 mg at 6 months, drug should be tapered over maximum one additional month for a maximum of 7 months.
- CR is reached with daily prednisone equivalent \leq 10mg/day. If CR is reached within <6 months, study drug is then tapered by 20 mg over one month.
- toxicity
- relapse of underlying malignancy
- progression of GVHD
- lack of response as defined by No Response in any organ system by Study Day 28
- voluntary withdrawal from study

Duration of Follow-Up

All patients will be followed for up to 6 months from initiation of study drug or 30 days from drug discontinuation (end of treatment, aka EOT) whichever is longer except in the cases of voluntary withdrawal from study or death.

For subjects who withdraw consent, there must be clear documentation of whether the subject withdraws consents to treatment only (i.e. agrees to follow-up) or withdraws consent to treatment and follow-up.

Follow-up

Follow-up appointments will entail review of concomitant medications, physical exam with vital signs, assessment of ECOG performance status, adverse event evaluation, GVHD staging, and assessment for relapse/survival. Labs will also be collected for complete blood count (CBC), comprehensive metabolic panel (CMP), coagulation labs (PT, aPTT, INR). Peripheral blood for PK, PD, ELISA, and immune reconstitution will be collected as above in the Study Calendar and in the Correlative Studies section (below). Patients will be followed weekly for the first two cycles of study drug and monthly thereafter until study drug discontinuation. Additional evaluations will occur at time of SAE or DLT, scheduled 6-month follow-up from initiation of study drug, and end of treatment (30 days from drug discontinuation). All follow-up will be done in-person with the exception of Cycle 2 Days 8, 15, and 22, which may optionally be done via secure video, per the physician's discretion.

Concomitant medications

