Of the 5 major CYP isoforms, 3A4 and 2C8 may be involved in Phase I metabolism of PLX51107, with possibly CYP2B6 and CYP2D6 playing a minor role. Until information regarding exposure-toxicity and exposure-response relationships are available with PLX51107, concomitant CYP3A4 and CYP2C8 inhibitors and/or inducers should be administered with caution in the event they alter the systemic exposure to PLX51107 (see Appendix for a list of strong CYP3A4/2C8 inhibitors and inducers). In general, strong inhibitors or inducers of CYP3A4 and CYP2C8 should be avoided unless absolutely necessary. These include anticonvulsants (phenytoin, carbamazepine, phenobarbital), mycin antimicrobials, azole antifungals and anti-retrovirals. Strong CYP3A4 and CYP2C8 inducers or inhibitors should be discontinued at least 14 days or 5 drug half-lives, whichever is longer, prior to the initiation of dosing with PLX51107, unless there is no alternative and the medication is absolutely necessary.

Should treatment with a strong CYP3A4 or strong CYP2C8 modulator be necessary, study drug should be discontinued during this time, and for at least 14 days or 5 drug half-lives afterwards, whichever is longer.

Concomitant medications are recommended as prophylaxis for nausea, vomiting, and infections, and are allowed for managing myelosuppression.

Initiation of QTc prolonging drugs should be performed with caution. QTc should be monitored closely with any new initiation or dose adjustment. Electrolytes should be monitored and repeated.

The concurrent use of systemic immunosuppressants commonly used for GVHD prophylaxis (calcineurin inhibition (tacrolimus, cyclosporine), mycophenolate, mofetil, and sirolimus) may enhance the immunosuppressant effects of PLX51107. Because the interactive effects of these drugs with PLX51107 are as yet unknown, proceed with caution and monitor drug

levels (tacrolimus cyclosporine, sirolimus) at minimum twice weekly and dose adjust as necessary to desired concentration

Steroids may be tapered based on starting steroid dose according to the below recommended schedule or per institutional guidelines:

% of Starting dose	Steroid Dose	Days	Number of days	% Decrease from previous dose
100%	1 mg/kg/day	Days 1-7	7	
75%	0.75 mg/kg/day	Days 8-14	7	25%
50%	0.5 mg/kg/day	Days 15-21	7	33%
25%	0.25 mg/kg/day	Days 22-28	7	50%
10%	0.2 mg/kg/day	Day \geq 29 and onwards		20%

% of Starting dose	Steroid Dose	Days	Number of days	% Decrease from previous dose

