100%	2 mg/kg/day	Days 1-7	7	
75%	1.5 mg/kg/day	Days 8-14	7	25%
50%	1 mg/kg/day	Days 15-21	7	33%
25%	0.5 mg/kg/day	Days 22-28	7	50%
13%	0.25 mg/kg/day	Days 28-35	7	50%
10%	0.2 mg/kg/day	Day \geq 36 and onwards		20%

Preparation, Reconstitution, and Dispensation

PLX51107 is an anticancer drug and, as with other potential toxic compounds, caution should be exercised when handling PLX51107.

Study Drug Packaging and Labeling

PLX51107 tablets are manufactured, packaged, and labeled according to current Good Manufacturing Practice (cGMP) at the following address:

BioDuro LLC (Formerly known as Formex LLC)
[name]
[name]

Storage and Handling

[figure not shown]
PLX51107 tablets should be stored at room temperature 20°C to 25°C (68°F–77°F); excursions permitted between 15°C and 30°C (59°F and 86°F). Subjects will be requested to store the study drug at the recommended storage conditions noted on the label.

The study drug provided in accordance with this protocol will be kept in a secure place and will only be supplied to subjects participating in this study. The Principal Investigator is accountable for all study drug in accordance with this protocol. In addition, the Principal Investigator must keep accurate and up-to-date dispensation records. Any study drug accidentally or deliberately destroyed must be recorded in a timely fashion, including an explanation for the destruction in writing. Any discrepancies between the amounts of study drug dispensed and returned must also be explained in writing.

All unused and partially used study drug must be sealed and returned to the Sponsor or designee, or destroyed on site in accordance with the established procedures for drug destruction. Details of destruction, including, but not limited to, the number of boxes destroyed, batch number, and the date and method of destruction must be recorded on the study drug destruction logs.

Correlative Studies

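### Both recommended steroid tapers end above the steroid limit in the CR stopping rule for any patient over 50 kg, and two entries in the taper tables contradict themselves

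*Combined protocol and SAP*

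**What the plan says.** Duration of Therapy, in the Treatment Plan, lists the events that end dosing. One is "CR is reached with daily prednisone equivalent" at or below 10 mg/day, a fixed daily amount that is not scaled to weight. The same bullet adds: "If CR is reached within <6 months, study drug is then tapered by 20 mg over one month". Another entry caps dosing at "6 months from initiation of study drug", with at most one further month of taper if the dose is then above 20 mg.

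Concomitant medications says: "Steroids may be tapered based on starting steroid dose according to the below recommended schedule or per institutional guidelines". Two tables follow, one for a 1 mg/kg start and one for a 2 mg/kg start.

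- **1 mg/kg table.** The last row reads "10% 0.2 mg/kg/day". It runs from Day 29 with no end day and gives a 20% decrease from the previous dose.
- **2 mg/kg table.** The last row is also 0.2 mg/kg/day, from Day 36 with no end day. The row before it reads "13% 0.25 mg/kg/day Days 28-35", and the row before that covers Days 22-28 at 0.5 mg/kg/day.

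The only steroid floor is 0.25 mg/kg daily, and it applies before Study Day 28 (Study Design; Investigational product).

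**The concern.** The stopping rule makes the steroid dose a condition for ending study drug after a complete response. The only schedule that the protocol prints should therefore reach that condition, or the protocol should say how a patient gets there. The schedule stops at a per-kilogram dose, the rule is a flat 10 mg/day, and nothing connects the two. For a patient in CR who stays on the printed schedule, time on PLX51107 could be set by the 6-month cap and not by response.

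Two entries in the tables also conflict with their neighbours. One percentage does not match its own mg/kg dose, and Day 28, the day on which CR and ORR are assessed, carries two different steroid doses.

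**Working it through.** **Inputs.** The 10 mg/day limit and the 6-month cap come from Duration of Therapy. The doses, percentages and day ranges come from the two tables in Concomitant medications. The table doses are read as prednisone equivalents, since their starting values match the 1-2 mg/kg prednisone range in Investigational product.

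**1. Reproducing the tables.** Percent of start = dose / starting dose. Percent decrease = 1 − dose / previous dose.

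| Table | Dose (mg/kg) | Printed % of start | Computed | Printed decrease | Computed |
|---|---|---|---|---|---|
| 1 mg/kg | 0.75 | 75% | 75% | 25% | 25% |
| 1 mg/kg | 0.5 | 50% | 50% | 33% | 33.3% |
| 1 mg/kg | 0.25 | 25% | 25% | 50% | 50% |
| 1 mg/kg | 0.2 | **10%** | **20%** | 20% | 20% |
| 2 mg/kg | 1.5 | 75% | 75% | 25% | 25% |
| 2 mg/kg | 1 | 50% | 50% | 33% | 33.3% |
| 2 mg/kg | 0.5 | 25% | 25% | 50% | 50% |
| 2 mg/kg | 0.25 | 13% | 12.5% | 50% | 50% |
| 2 mg/kg | 0.2 | 10% | 10% | 20% | 20% |

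After rounding, one entry fails: the 10% label in the 1 mg/kg table. The other two figures in that row agree with each other, since 1 − 0.2/0.25 = 20%. A true 10% step would be 0.1 mg/kg, a decrease of 1 − 0.1/0.25 = 60%, which is not what the row prints.

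**2. Last row against the exit condition.** Largest weight that satisfies the limit = 10 mg / (dose in mg/kg).

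- At 0.2 mg/kg: 10 / 0.2 = 50 kg.
- At 51 kg: 0.2 × 51 = 10.2 mg/day.
- At 70 kg: 0.2 × 70 = 14 mg/day.
- At 100 kg: 0.2 × 100 = 20 mg/day.

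The result is the same for both starting doses because both tables end at 0.2 mg/kg. It does not depend on the wrong label, so correcting the label alone leaves the gap in place.

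**3. Possible extra time on drug.** Suppose CR is present around Day 29, about month 1. If the CR exit applied then, with its one-month taper, drug would stop at about month 2. If the exit is not met, drug continues to month 6, or to month 7 with the permitted taper. The difference is 6 − 2 = 4 to 7 − 2 = 5 months. This is an upper scenario: it needs sustained CR, no steroid dose below the last row, and no other reason for stopping.

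**4. Day 28 in the 2 mg/kg table.** Days 28-35 inclusive is 35 − 28 + 1 = 8 days, printed as 7. Day 28 is therefore in the 0.5 mg/kg row and also in the 0.25 mg/kg row, a two-fold difference (35 against 17.5 mg/day at 70 kg). The 0.25 mg/kg floor does not settle which row applies, because it covers only the days before Day 28 and both doses meet it.

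**The case against.** The strongest answer is that the tables are a recommendation. Sites may taper "according to the below recommended schedule or per institutional guidelines", and no floor is stated from Day 28 on, so nothing prevents a patient of any weight from reaching 10 mg/day. On that view the two sections do not strictly contradict each other: one sets a joint condition, and the other is a suggested schedule that stops short of it. This stands, and it limits the point to patients who stay on the last printed row.

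A reader might infer more, in four ways that the documents do not support.

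- **That the wrong label decides whether adults between 51 and 100 kg can leave on CR.** At 0.1 mg/kg the weight limit would be 10 / 0.1 = 100 kg. However, the mg/kg and decrease columns both point to 0.2 mg/kg. The 10% figure equals the correct label in the 2 mg/kg table, so a carry-over is plausible, though that is an inference. The 2 mg/kg table has no label conflict at all, and the optional taper means that neither figure decides what a patient can reach.
- **That the Day 28 overlap alters CR or ORR.** GVHD Response Definitions contains no steroid condition. The overlap changes the background steroid dose on the assessment day, not how response is scored. The printed 7 days and the next row's start at Day 36 also suggest a simple boundary slip.
- **That 6-month NRM or late toxicity will differ by taper.** The documents give no institutional taper and no figure from which to derive such an effect.
- **That dose finding is affected.** DLT and biological activity are observed over the first 28 days, before the final row begins on Day 29 or Day 36.

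**Conclusion.** The point holds in a limited form. Each recommended taper ends at a dose that exceeds the CR stopping rule's 10 mg/day for every patient above 50 kg. A patient in CR who stays on that row would not meet the CR exit and could remain on PLX51107 to the 6-month limit, at most about 4 to 5 months longer than with an exit near Day 29. This assumes that the last row is followed without further reduction, and that the sentence on tapering study drug after CR carries the same steroid condition as the rest of its bullet. The documents give no weights and no count of sites using the printed schedule, so the share of patients affected cannot be stated.

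The two table errors are certain but small: 10% printed where 0.2 / 1 = 20%, and Day 28 assigned to two rows with an 8-day range labelled 7. These are operative tables tied to a study-drug stopping rule, so they should be put right.

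**What to change.** The sponsor should reconcile three places, choosing the doses and the rule itself:

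1. The percentage and the mg/kg dose in the last row of the 1 mg/kg table.
2. The row boundaries in the 2 mg/kg table, so that Day 28 has one assigned dose and the day count matches the range.
3. The open-ended last step of both schedules and the steroid condition in Duration of Therapy, so that the protocol makes clear how a patient in CR on the recommended schedule is to be handled.

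No dose or stopping criterion is proposed here. Separately, the prednisone-equivalent dose at Day 28 and at CR exit could be reported alongside CR. The Study Calendar lists a concomitant medication review but does not say that it records dose, so this should be confirmed first.

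The cost is wording in two tables and one bullet, plus one case report form field if steroid dose is not already recorded. Sample size, endpoints and the dose-escalation rules do not change.

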[figure not shown]
Study Design

This is a Phase 1, open-label, single-center, dose-finding study to evaluate the safety, tolerability, and biologically effective and tolerable dose (BETD) of PLX51107 in combination with corticosteroids in treatment-refractory acute GVHD patients. The dose cohorts are as outlined in Table 1. We will determine the dose of PLX51107 that both shows biological activity (BA) and is tolerable when used in combination with corticosteroids. BA is assessed by pharmacokinetics (PK) for target exposure of AUC_{0-24} 8300 ng•hr/mL at Day 1 based on preclinical in vivo pharmacological efficacy studies (PLX51107 IB).

All diseases, transplant and donor types are included. PLX51107 will be administered orally daily as tolerated. All patients will concurrently receive prednisone 1mg/kg orally daily (may be divided into 2 doses) or MP IV equivalent. Corticosteroids may be tapered per institutional

guidelines, but taper may not be initiated sooner than 7 days after Study Day 1 and to no less than prednisone 0.25mg/kg daily before Study Day 28. We will further assess biological activity as compared across clinical responses at different dose levels to determine the recommended Phase 2 dose (RP2D) for additional evaluation.

Figure 5. Study schematic

The observation period for DLT and BA will be the first cycle of 28 days. A dose level will be deemed the BETD if 5 or more out of 6 patients demonstrate a BA with 0-1 DLTs. This dose will be declared biologically effective and tolerable. The starting dose level is at Dose Level 1 (40 mg/day). Refer to Table 1 for Dose Levels.

This study design combines a standard rule-based Phase 1 3+3 trial design that simultaneously evaluates tolerability (DLTs) and evidence of biological activity at each dose level. Three patients are entered at each dose level and expanded to six patients if sufficient tolerability and BA is observed. See Figure 1 for a study schematic. If 2 or more patients at a given dose level

experiences DLT, accrual at that dose level will stop, and the dose level will be de-escalated. If at the lowest dose level, accrual will be suspended and the study terminated.

After BETD is determined, we will review the tolerability, biological activity, and clinical responses observed to justify a RP2D.

Table 1. Dose levels

Cohort	Dose level (mg/day)
0	20
1 (initial)	40
2	80
3	120

Statistical analysis plan:

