APPENDIX 1: CYP3A4/CYP2C8 INHIBITORS AND/OR INDUCERS

Strong CYP3A4 and/or CYP2C8 inhibitors and/or inducers and CYP2D6 substrates with a narrow therapeutic index

CYP3A4 and/or CYP2C8 Strong Inhibitors

- Protease inhibitors
 - Ritonavir
 - Indinavir
 - Nelfinavir
- Macrolide antibiotics
 - Erythromycin
 - Telithromycin
 - Clarithromycin
- Azole antifungals
 - Voriconazole
 - Ketoconazole
 - Itraconazole
- Chloramphenicol (antibiotic)
- Nefazodone (antidepressant)
- Bergamottin (constituent of grapefruit juice)
- Aprepitant (antiemetic)
- Verapamil (calcium channel blocker)
- Gemfibrozil (hypolipidemic)
- Thiazolidinedione (antidiabetic)
- Montelukast (Leukotriene receptor antagonist)
- Quercetin (anti-inflammatory)

CYP3A4 and/or CYP2C8 Strong Inducers

- Anticonvulsants, mood stabilizers
 - Phenytoin
 - Carbamazepine
 - Oxcarbazepine
- Non-nucleoside reverse transcriptase inhibitors
 - Efavirenz
 - Nevirapine
 - Etravirine
- Phenobarbital (barbiturate)
- Rifampicin (bactericidal)
- Modafinil (stimulant)
- Hyperforin (constituent of St John's Wort)
- Cyproterone (antiandrogen, progestin)

CYP2D6 Substrates

- Amiodarone
- Dosulepin
- Flecainide
- Sotalol
- Pimozide
- Procainamide
- Theophylline

This list is not comprehensive and subject to change and all medications should be reviewed prior to administering.

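### The rules on strong CYP3A4/2C8 modulators at the start of PLX51107 and during treatment are not reconciled, and a Day 1 AUC taken on a modulator still counts toward the 5-of-6 biological-activity rule

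*Combined protocol and SAP*

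**What the plan says.** Concomitant medications gives a metabolic reason for caution: "3A4 and 2C8 may be involved in Phase I metabolism of PLX51107". Inhibitors and inducers of these enzymes "should be administered with caution in the event they alter the systemic exposure to PLX51107". No fold change is stated.

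Three rules on strong modulators follow.

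- **General rule:** "strong inhibitors or inducers of CYP3A4 and CYP2C8 should be avoided unless absolutely necessary".
- **Start rule:** they are stopped at least 14 days or 5 half-lives (the longer) "prior to the initiation of dosing with PLX51107, unless there is no alternative and the medication is absolutely necessary".
- **Stop rule, next paragraph:** "Should treatment with a strong CYP3A4 or strong CYP2C8 modulator be necessary, study drug should be discontinued during this time". The interruption then continues after the modulator ends, for a minimum of 14 days or 5 half-lives (the longer).

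The same section adds: "Concomitant medications are recommended as prophylaxis for nausea, vomiting, and infections". It names azole antifungals among the agents to avoid. Appendix 1 lists voriconazole and aprepitant, an antiemetic, as strong inhibitors. No inclusion or exclusion criterion mentions modulators.

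On the endpoint, Study Design says "BA is assessed by pharmacokinetics (PK) for target exposure of" AUC0-24 8300 ng·hr/mL at Day 1. A dose level becomes the BETD when at least 5 of 6 patients show BA with no more than one DLT. Correlative Studies plans a separate PK analysis for GI GVHD because of possible malabsorption, and none by modulator use. Dosing Delays or Missed Doses replaces patients only when more than 7 of the first 28 doses are missed through noncompliance.

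**The concern.** There are two linked problems.

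First, a patient admitted under the start exception is by definition someone for whom the modulator is necessary. Read literally, that patient meets the stop condition on Day 1. Two investigators could treat the same patient differently and both cite the protocol. If the stop rule is applied in Cycle 1, doses are missed for a reason the replacement rule does not cover.

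Second, if such a patient is dosed, the Day 1 AUC enters the BA count like any other. An inhibitor could lift it over 8300 and an inducer could hold it below, and either result would be credited to or held against the dose level. BETD is a primary endpoint decided on six patients, so the cohort's co-medication could influence which dose is declared. The protocol already recognises one exposure confounder, malabsorption in GI GVHD, but gives this one no analysis rule.

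**Working it through.** The plan states no figure on this point, so there is nothing to reproduce. The check asks how far modulator use could move the 5-of-6 rule.

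**Inputs from the documents.** Target 8300; rule at least 5 of 6; doses 40, 80 and 120 mg. The earlier human PK table (Background) gives Day 1 AUC0-24 of 16200 at 160 mg and 29100 at 240 mg. The column heads are missing from the available text, but the reading agrees with the ratio printed at the end of each row: 11300/16200 = 0.70 and 18900/29100 = 0.65.

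- 16200/160 = 101 ng·hr/mL per mg
- 29100/240 = 121 ng·hr/mL per mg

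Under dose proportionality the typical Day 1 AUC is 40 × 101 to 40 × 121 = 4040–4840 at 40 mg, 8080–9680 at 80 mg and 12120–14520 at 120 mg. The 80 mg level sits almost on the target.

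**Assumptions not in the documents.** Dose proportionality; lognormal AUC with the table value as median; between-patient CV 40% or 60%; inhibitor effect f = 1.5 or 2.

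**Per-patient probability.** With σ = √ln(1 + CV²), which is 0.385 or 0.555,

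P(BA) = 1 − Φ( ln[8300 / (dose × AUC per mg × f)] / σ ).

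Example, 80 mg, 101 per mg, CV 40%:

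- Unexposed: ln(8300/8080)/0.385 = 0.07, so p0 = 0.472.
- f = 2: ln(8300/16160)/0.385 = −1.73, so p1 = 0.958.

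**Cohort probability.** With nobody exposed it is 6·p0⁵(1 − p0) + p0⁶ = 0.085. With one exposed it is p1·[5·p0⁴(1 − p0) + p0⁵] + (1 − p1)·p0⁵ = 0.958 × 0.155 + 0.042 × 0.023 = 0.149. With exactly three exposed, the same exact sum is taken over three patients at p1 and three at p0.

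Ranges over CV 40–60% and f = 1.5–2, for P(at least 5 of 6):

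| Dose and AUC per mg | None exposed | One exposed | Three exposed |
|---|---|---|---|
| 80 mg, 101 | 0.085–0.092 | 0.13–0.15 | 0.25–0.42 |
| 80 mg, 121 | 0.25–0.33 | 0.31–0.43 | 0.47–0.71 |
| 40 mg, 101–121 | below 0.001 | at most 0.002 | at most 0.02 |
| 120 mg, 101–121 | 0.54–0.93 | 0.61–0.95 | 0.75–0.98 |

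**Inducers.** If an inducer halves AUC (f = 0.5, also assumed), one exposed patient at 80 mg lowers the chance to 0.03–0.04 at 101 per mg, or 0.13–0.15 at 121 per mg. Three exposed patients lower it to at most 0.02.

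**The case against.** **The two rules may not conflict.** The start rule speaks of drugs in use before dosing, and discontinuing study drug presupposes a patient already on it. One rule could therefore cover pre-existing modulators and the other those begun on study. That reading is possible, but the text does not draw the line. The point stands as a request for reconciliation, not as proof that no consistent reading exists.

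**Exposure should be rare.** A reader might infer from the prophylaxis sentence and Appendix 1 that the conflict is bound to arise. The documents do not support that: the sentence names no drug, and azoles are expressly among the agents to avoid. Washout is the default and the exception is narrow. One exposed patient per cohort fits the text better than three, and its effect is modest.

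**The AUC is real.** An AUC reached on an inhibitor is not a false measurement. The exposure was achieved; what is doubtful is crediting it to the dose. The documents say only that these enzymes may be involved, so the interaction could be small.

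**The BETD is not the last word.** Tolerability, biological activity and clinical responses are reviewed before a recommended Phase 2 dose is justified, and Day 8 and Day 15 PK can inform that review. This softens the consequence but leaves the primary endpoint rule as it is.

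**Conclusion.** The point holds in two limited parts. The start exception and the stop rule do not say how they fit together. The BA rule does not say what to do with a Day 1 AUC taken on a modulator.

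The effect depends on dose. It is largest at 80 mg, where the projected AUC lies near 8300: one exposed patient raises the chance of meeting the BA criterion by about 4 to 6 percentage points at 101 per mg (for example 0.085 to 0.149), and by 6 to 11 points at 121 per mg. At 40 mg it is negligible. At 120 mg the criterion is already more likely than not to be met without exposure. The three-exposed column is a stress case, not a forecast. A reader might infer that the BETD will be wrong; nothing in the documents establishes how often modulators would be used or how strongly they act.

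All probabilities rest on the assumed fold changes and CVs, dose proportionality and a lognormal AUC. The text under Withdrawal and the opening of the human PK table were not available; nothing in the remaining text resolves either part.

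**What to change.** 1. The sponsor should reconcile the start exception, the stop rule, the prophylaxis recommendation and Appendix 1, and state which patients each rule covers. Which clinical rule applies is for the sponsor to decide.

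2. However that is settled, add to the BA definition in Study Design: a Day 1 AUC0-24 from a patient with a strong CYP3A4 or CYP2C8 modulator within the protocol's own washout (14 days or 5 half-lives, whichever is longer) is flagged, reported separately and not counted toward the 5-of-6 BA criterion. Such patients stay in the DLT and safety evaluation.

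3. Extend the replacement rule under Dosing Delays or Missed Doses, which now covers only noncompliance, to say how these patients are replaced for BA.

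The cost is protocol wording and a flag drawn from the concomitant medication review already scheduled at Screening. The downside is that an occasional patient will not be evaluable for BA, and replacing that patient may take accrual above the stated maximum of 18. Number of Subjects should allow for this.
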